4.0 Rockefeller University Conflict of Interest

4.1 **Investigator Financial Conflict of Interest** All KSP (unless they have done so in the past 12 months) must complete and update promptly a Rockefeller University Significant Financial Interest Disclosure at <http://mycoi.rockefeller.edu/>. Prompt disclosure means within 30 days of discovering or acquiring a Significant Financial Interest, and as early as possible in the development of this protocol. If a KSP discloses a significant financial interest that may constitute a conflict of interest with respect to the proposed study, he or she must E-mail a copy of the Lay Summary of the study to [name] ([contact]). Doing so will allow the process of addressing the potential COI to proceed in step with the development of the study protocol. Tardiness or non-compliance with this requirement will very likely cause delay in submission of the study for IRB review. **Institutional Conflict of Interest** As early as possible the PI or designee preparing this application must log in to <https://icoi.rockefeller.edu/account/login.php>, which lists entities in which The Rockefeller University has a direct financial interest. If the proposed study involves any entity on that list the PI or designee must E-mail the entity involved and a copy of the Lay Summary to [name] so that the process of addressing the potential Institutional COI can proceed in step with the development of the study protocol.

7.0 Study Description

7.1 * Lay Summary

Please provide a summary of your study in lay language. The summary should be no more than a half page (500 words or less) and should contain a clear statement of the rationale for the study.

Inflammation of fat stores is emerging as an important factor in the complications of obesity including type 2 diabetes and in the development and outcome of breast and colon cancers. This inflammation increases the amount of a substance, prostaglandin, which then can stimulate other factors that lead to obesity complications. Prostaglandin (PGE-2) is converted into another prostaglandin (PGE-M) which is excreted in the urine in amounts that reflect the amount of prostaglandins in the body. Inflammation in fat stores also increases the amount and activity of aromatase, an enzyme whose action results in increased estrogen and its metabolites in fat tissues, the blood, and the urine. Increased estrogen is important in postmenopausal obese women in whom the incidence and the spread of breast cancer is increased by estrogen. In addition, inflammation in fat tissues of obese women results in the formation of a characteristic histologic structure called the "crown-like structure" which reflects the death of adipose tissue cells surrounded by accumulated pro-inflammatory cells called macrophages.

Prostaglandins in the body are inhibited by a class of medicines called non-steroidal anti-inflammatory drugs which include aspirin and Advil (with potential bleeding side effects) but also by Celebrex which increases bleeding very little. This medicine is being used by patients with arthritis conditions. We plan to provide Celebrex before and after collecting blood, urine, and abdominal fat tissue (by biopsy) to examine how effective the medicine may be in reducing inflammation, crown-like structures in fat tissue, the enzyme aromatase, PGE-M in the urine and estrogen in blood and urine. Volunteer subjects will be expected to stay in the hospital for about 3 weeks taking Celebrex for approximately 10 days while eating a diet similar to what they consumed before coming into the hospital for the study. The study plans to find out whether Celebrex may be potentially useful to decrease inflammation in fat tissues and thereby lower the production of substances such as estrogens that may increase the risk of developing breast cancer and lead to a poor outcome of the disease.

7.2*** Public Health Impact Statement**

Provide a brief plain language statement (100 words or less) of the value of the research proposed and its potential impact on population health. Additional instructions located in Help.

Post-menopausal breast cancer is a common disease in the Western world. Celecoxib as an NSAID would be expected to reduce inflammation in adipose tissue including in the breast. Reduction of such inflammation should lower the risk of breast cancer. No directed study of NSAID effect on inflamed adipose tissue has been performed in humans previously for breast cancer therapy. This study has the potential to further future breast cancer treatment.

7.3*** Submission Request Category**

Please indicate:

Expedited Review

8.0**Screening for Expedited Review****8.1**

Studies that may be reviewed by expedited review fall into 7 categories described in detail in 46CFR 8392. These include drawing of blood within prescribed limits, collection of samples such as saliva, mucosal and skin cells by scraping, and excreta or sweat. Data may be collected by physical sensors such as weighing, EKG, EEG, MRI, moderate exercise and strength testing, and body composition assessment. Collection of data from voice, video or image recordings obtained in research. Research on perception, cognition, social behavior employing surveys, interviews, focus groups and oral history.

Research may be conducted on data, documents, records or specimens that have or will be collected solely for non-research purposes in the course of medical treatment or diagnosis.

Note: Protocols that involve a drug that requires an IND, or that involve greater than minimal risk to subjects or that involve the use of X-rays or microwaves are not eligible for an expedited review.

* Based on the above information, does your research study qualify for an "expedited" review?

- Yes
- No
- Not Sure

9.0

Clinical Trial Registration

9.1

Clinical Trial Registration

The types of studies listed below must be registered at www.ClinicalTrials.gov

- Study involves testing of FDA regulated drugs or biologics (See HELP)
- Study is funded by the NIH, and meets the definition of a "clinical trial" (see HELP)
- Study meets the ICMJE definition of a "clinical trial" (See HELP)
- None of the above

If you selected 1, 2, or 3, you must register your trial with ClinicalTrials.gov through the Rockefeller University institutional account. Please contact the Clinical Research Support Office [name] for assistance.

10.0

Study Overview/Summary

10.1 * Who initiated this study?

Please specify one:

- Principal Investigator Initiated
- Industry Initiated
- Other

If other, please specify:

10.2 * This study in collaboration with:

- Weill Cornell Medical College
- Memorial Sloan-Kettering Cancer Center
- Both Weill Cornell Medical College and Memorial Sloan-Kettering Cancer Center
- Neither Weill Cornell Medical College nor Memorial Sloan-Kettering Cancer Center

Please note: If any of the first three options is checked, you will be prompted to attach the **Tri-Institutional Study Specific Financial Disclosure** and the **IRB of Record** forms later on in the submission. Links to these forms can be found in the Help link to the right.

10.3 * Are other institutions involved in the study?

- 1. No
- 2. Yes, and a federal, industry or private organization is administratively coordinating the study.
- 3. Yes, however, a federal, industry or private organization is not administratively coordinating the study.

If #3 was selected above, please provide the following for each involved institution:

Name of Other Institution	Date of Approval by Other Institution	Date of Pending Approval by Other Institution	Date of Expiration at Other Institution
WCMC	03/10/2014		03/05/2015
MSKCC	04/23/2013		

10.4 * Is this a multi-center trial?

Yes No

10.5 * Who (What) is to be studied?

- Human Subjects - including coded samples and/or data with links to Identifiers
- Deidentified Samples - unable to be linked to identifiers by receiver
- Data Only - unable to be linked to identifiers

10.6 *Study Type:

- Interventional
- Observational

10.7 The initial date of IRB approval was:

04/04/2013

10.8 * What is the expected duration of the study?

3 years

10.9 * Are any of the following agents to be used in the study?

Check all that apply:

- Drug FDA Approved
- Approved Drug for Off-Label Purpose
- Investigational New Drug
- Biologic Agents
- Nutritional Supplements
- Placebo
- Vaccines
- No Agents

10.10 * Are investigational devices to be used in the study?

Yes No

If Yes, please specify:

- A Significant Risk Device
- A Non-significant Risk Device

10.11 Special Research Procedures

Does the study propose to directly involve participants in the following special research procedures?

- Recombinant DNA
- Gene Therapy

If either item is checked, please see Help for details.

10.12 * Radioactive Isotopes Involved

Will subjects be exposed to any radiation other than routine x-rays solely for clinical care purposes?

- Yes
- No

11.0 Interventional

11.1 *Interventional, please specify:

- Open Label
- Single Blind
- Double Blind
- Other

If Other, specify:

12.0 Objectives and Rationale

12.1 * Overview

Briefly state the **purpose of this study**. Give enough background and rationale to provide both scientists and lay members of the IRB and ACCTS with the basis for exposing human subjects to the risks involved.

Obesity increases the risk for the development of and the progression to metastasis of numerous malignancies including hormone receptor-positive breast cancer in postmenopausal women (1). Medications that suppress the biosynthesis of estrogen or block its actions decrease the risk of hormone receptor-positive breast cancer (2). In obese women, inflammation manifested as crown-like structures (CLS), is associated with NF- κ B-dependent induction of proinflammatory mediators including TNF- α , IL-1 β , IL-6 and COX-2-derived PGE₂ in breast white adipose tissue (3). Moreover, increased levels of aromatase, the rate-limiting enzyme for estrogen synthesis, are found in association with elevated levels of proinflammatory mediators in breast white adipose tissue (4). This finding is consistent with extensive evidence that proinflammatory mediators, including PGE₂, induce aromatase expression (5-6). Importantly, we have evidence that it is common for inflammation to occur in both breast and abdominal subcutaneous white adipose tissue, in parallel, in obese women making abdominal subcutaneous white adipose tissue a useful surrogate tissue to study.

If reductions in subcutaneous adipose tissues of the inflammatory markers to be studied and aromatase levels directly correlate with reduced urinary excretion of PGE-M, an index of prostaglandin activity in the body, then this will support direct effects of Celecoxib upon adipose tissue inflammation as a mechanism and also will underlie the use of urinary PGE-M determinations as a biomarker reflecting changes in adipose tissue inflammation.

The potential use of celecoxib in modulating aromatase activity is supported by epidemiologic evidence that chronic use of nonsteroidal anti-inflammatory drugs (NSAIDs), prototypic inhibitors of PGE₂ synthesis, decrease levels of circulating estrogens and reduce the risk of breast cancer (7). In addition, increasing numbers of studies have suggested that other complications of obesity including cardiovascular disease and type 2 diabetes mellitus are related to inflammatory activity in adipose tissue.

We plan to study circulating levels of estradiol and estrogen metabolites and the urinary excretion of estrogen metabolites to establish whether this dose of celecoxib, by reducing aromatase, actually alters estrogen metabolism as hypothesized if adipose tissue inflammation is reduced. Direct demonstration of such a change in estradiol and estrogen metabolism should point to the importance of reducing adipose tissue inflammation in obese post-menopausal women in order to reduce the risk and the spread of estrogen receptor positive breast cancer in such patients.

Obesity is associated with elevated levels of urinary PGE-M, a biomarker that reflects increased systemic levels of PGE₂. We hypothesize that treatment with celecoxib, a selective COX-2 inhibitor, will reduce levels of PGE₂ and aromatase in inflamed abdominal subcutaneous white adipose tissue of obese postmenopausal women. This concept is supported by preclinical evidence that celecoxib suppressed PGE₂ levels and aromatase activity in the mammary glands of obese mice (Fig. 1). Celecoxib also suppressed the elevated levels of urinary PGE-M found in obese mice (Fig. 2). Based on this constellation of findings, we speculate that celecoxib-mediated decreases in levels of urinary PGE-M will correlate with reduced levels of PGE₂ and aromatase expression in abdominal subcutaneous white adipose tissue of obese postmenopausal women. Celecoxib is the preferred agent for these studies because it does not have the anti-platelet activity that traditional NSAIDs possess. Hence, biopsies of abdominal subcutaneous white adipose tissue can be done without a medication-related increased risk of bleeding.

The results of this study could be important for highlighting the potential benefit of NSAIDs for reducing the risk of hormone receptor-positive breast cancer in obese postmenopausal women, a growing segment of the population.

Significance

The use of NSAIDs has been associated with a reduced risk and spread of colorectal cancer. Most epidemiological studies suggest that use of NSAIDs also is associated with a reduced risk and spread of breast cancer although the protective effects are more modest. We speculate that this class of medication like others will be effective in some but not all individuals to reduce breast cancer risk. In particular, we hypothesize that these agents will be of benefit if used chronically in the up to 75% of obese postmenopausal women who demonstrate white adipose tissue inflammation and CLS. If Celecoxib suppresses levels of inflammation and aromatase in abdominal white adipose tissue which is likely to mirror what occurs in breast white adipose tissue, this would suggest that chronic use of NSAIDs is likely to reduce the risk and spread of hormone receptor-positive breast cancer in this growing segment of the population. Importantly, if reduction in urinary PGE-M reflects reduction in adipose tissue inflammation this would be a useful non-invasive marker for this property in future studies.

We additionally plan to study the fecal microbiota of 5 of the 10 participants being studied.

Studies on metabolic diseases such as obesity during the past few years have included important consideration of the impact of changes in the colonic microbiome. Indeed, several of our recent studies at The Rockefeller University Hospital have included a collection and storage of fecal specimens for later analysis. We, in collaboration with [name] at Cornell have established a relationship with [name] at MSKCC who is willing to perform analysis on specimens that were collected immediately before and after 10% weight loss in obese volunteers (PHO 785).

Our metabolic studies usually have been performed in small groups of subjects who are studied while consuming a preselected diet before and after an intervention.

As we plan similar studies, it has become evident that we do not know how soon after admission to RU and initiating a Bionutrition Department provided diet should fecal specimen collection be initiated as a stable baseline before starting the intervention. Previously, we only have used 3 days before the intervention based on scant data in the literature. We now believe that it is very important to determine how long it takes under the condition of our studies at RUH to establish reasonable fecal microbiota stability.

Available information suggests that there are 3 predominant microbe enterotypes described initially in 2011 (20). Studies in 5 subjects consuming either a high fat/low fiber or a low fat/high fiber diet in a single study suggested that the distinct differences between individual subjects generally were maintained over 10 days after an abrupt change in the 1st 24 hours. No switching in the primary 3 enterotypes was detected within 1 week of the diets (21).

In a study of Malawi twins, discordant for kwashiorkor, administration of a therapeutic food supplement resulted in modest but non significant changes in the fecal microbiota in 2 weeks (22).

A much quoted study by Faith et al evaluated the stability of the fecal microbiome up to 5 years showing that up to 60% of the individual species remained stable (23). However, weight loss impaired microbiota stability in studies performed before and after 8 weeks of a low calorie diet.

In our present studies, we had taken fecal samples 2-3 days after the RUH admission and the start of a diet designed by our Bionutrition Department that mimicked each subject's pre-study diet and then initiated the intervention. However, on the basis of the available information, we do not know how long to administer such a diet before taking the initial fecal sample prior to the medical intervention such as Celecoxib. The present proposed study will determine whether the fecal microbiota is stable after 3 or 7 days or needs 14 or more days. This information will guide our procedures in future similar studies.

12.2 * Engaging Stakeholders: Describe any plans to engage other stakeholders (Scientists, practitioners, patients, advocacy groups, etc.) for hypothesis generation, or feasibility purposes.

[name] who will perform several analyses of adipose tissue pertaining to effects of Celecoxib on the aromatase enzyme. [name] and [name] who will perform microbiome studies that aim to determine whether Celecoxib alters fecal microbiota composition and whether a self-selected diet mimicking a subject's pre-study long-term diet will keep fecal microbiota composition constant.

12.3 * Hypothesis

Describe the **research hypothesis** in a single sentence.

Celecoxib, an inhibitor of cyclooxygenase-2 (COX-2) will reduce urinary excretion of PGE-M, and suppress levels of prostaglandin E₂ (PGE₂) and aromatase in inflamed abdominal subcutaneous adipose tissue in grade 2-3 obese postmenopausal women.

12.4 * Aim(s)

Indicate how you will **address the hypothesis** (e.g., to compare groups, to estimate a parameter, to ascertain feasibility). Since the sample size determination is usually based on the primary aim only, the primary aim should be sufficient to justify the study.

To determine whether oral administration of celecoxib 200 mg BID to grade 2-3 obese postmenopausal women will significantly reduce the excretion of PGE-M in the urine.

12.5 * Primary Outcome(s)

Indicate which **variable(s)** will be assessed to judge the primary specific aim. Give measurement units, if applicable.

PGE-M in urine will be significantly reduced

12.6 * Secondary Outcome(s)

Indicate which **additional variable(s)** will be assessed to judge the secondary outcome(s). Give measurement units, if applicable.

Crown-like structures in subcutaneous adipose tissue

PGE₂ in subcutaneous adipose tissue

aromatase in subcutaneous adipose tissue biopsies and crown-like structures in subcutaneous adipose tissue

Circulating levels of TNF- α , IL-6, IL-8, and MCP-1.

Levels of circulating serum estradiol and selected estrogen metabolites in serum and urine

Determination of the length of time to achieve stability of fecal microbiota

Serum endocannabinoid concentration at baseline (Days 3 and 14) , Day 13 & 24, and Outpatient End of study visit

12.7 * Methods and Procedures

Please provide a description of the laboratory and clinical analyses and procedures that will be performed. Include the role of external collaborators and consultants when appropriate.

This is a pilot study of 10 grade 2-3 (BMI between 35-50) obese postmenopausal women to determine if treatment with Celecoxib 200 mg bid for 10+-1 days leads to reduced levels of abdominal subcutaneous white adipose tissue PGE₂, and aromatase activity in association with decreased levels of urinary PGE-

M. Previous studies (17) have shown that this interval is sufficient to achieve steady state circulating levels of the drug and to significantly suppress urinary PGE-M levels.

Two screening visits will take place in the OPRC and the remainder of the study will be an in-patient study in which the participants may leave RUH for periods of time during the day, unless it is a "testing" day.

Patients will be given a 3-day rotating diet based on their regular diet as reported and reviewed with the bionutrition department.

5 out of the 10 participants recruited will be asked to be admitted to the Rockefeller University Hospital IPU 11 days earlier (2 weeks prior to Celecoxib administration) for a total of 24 inpatient days in order to determine stabilization time for fecal microbiota. 4 additional stool samples will be collected at Days 0,3, 7, and 11, +/- 1 day.

Screening Visit #1

Informed consent

Medical History and Physical exam

EKG

Waist measurement

Distribution of 3-day food diary

HIV POCT

Subjects will be instructed to fast 10 hours prior to their next visit for fasting labs.

Subjects will be instructed to discontinue taking over the counter medications (OTCs). Those subjects which require medication for relief of pain will be advised to use only Tylenol and given a week's supply.

Screening visit #2

Return of 3 day food diary

Fasting labs to include- CBC/Diff, ESR, Comprehensive Metabolic Panel, Thyroid Stimulating Hormone, lipid profile, hsCRP, PT/PTT/INR, serum estradiol

Bionutrition consult to review the 3 day food diary and determine subject's "usual diet"

A clinic meal will be provided after labs are drawn.

Dispense Tylenol 325 mg #30, 2 tablets by mouth as needed for pain.

Eligibility will be determined following lab results. Subjects will be scheduled for admission within 1-4 weeks of their screening. If greater than 1 month has passed from screening, safety labs (CBC/DIFF, CMP, PT/PTT/INR) will be re-drawn prior to admission.

Inpatient Admission

Day 0

Admit to RUH at approximately 11 AM

Study diet lunch and dinner

Day 1

Usual diet

Day 2

Spot urine for PGE-M

24 hour urine for testing of the following: PGE-M, estrogen metabolites, creatinine, volume stool sample +/- 1 day

NPO after 9 pm except water

Day 3

Fasting research labs- TNF- α , IL6, IL8, MCP-1, insulin, serum estradiol and estrogen metabolites, serum endocannabinoids

MSKCC labs: CBC, ESR, CMP, hsCRP, PT/PTT/INR, lipid panel, estradiol

Spot urine for PGE-M after completion of 24-hr urine collection

Fat biopsy

Start Celecoxib 200 mg PO BID

NPO after 9 pm except water

Day 4

Bod Pod

Continue Celecoxib 200 mg PO BID

Day 5

Usual diet

Continue Celecoxib 200 mg PO BID

Day 6

Usual diet

Continue Celecoxib 200 mg PO BID

Day 7

Usual diet

Continue Celecoxib 200 mg PO BID

Day 8

Usual diet

Continue Celecoxib 200 mg PO BID

Day 9

Usual diet

Continue Celecoxib 200 mg PO BID

Day 10

Usual diet

Continue Celecoxib 200mgPO BID

Day 11

Usual diet

Continue Celecoxib 200mg PO BID

Day 12

Spot urine for PGE-M

24 hour urine for testing of the following: PGE-M, estrogen metabolites, creatinine, volume stool specimen +/- 1 day

Continue Celecoxib 200 mg PO BID

NPO after 9 pm except water

Day 13

Celecoxib 200 mg PO in AM

Fasting research lab: TNF- α , IL6, IL8, MCP-1, insulin, serum estradiol and estrogen metabolites, celecoxib level, serum endocannabinoids

MSKCC labs: CBC, ESR, CMP, PT/PTT/INR, hsCRP, lipid panel, estradiol

Spot urine for PGE-M after completion of 24 hour urine collection

Fat biopsy

Usual diet

Discharge from RUH

Dispense Tylenol 325mg #30 tablets.

Upon discharge, tylenol will be provided 325 mg PO #30 (to be taken PRN)

Subjects will be instructed not to take any NSAIDs until their next visit. Tylenol will be provided to reinforce the need to avoid the use of NSAIDs for intercurrent mild discomfort such as intercurrent headaches or influenza-like symptoms and to substitute tylenol. This precaution is taken to prevent distortion of urine PGE-M to be collected 10 days after cessation of Celecoxib administration.

Out-Patient Visit:

End of study visit (7-11 days after discharge)

Spot urine collection for PGE-M

Research labs: serum estradiol and estrogen metabolites, serum endocannabinoids

MSKCC labs: hsCRP, estradiol

Stool collection- Patients will be given a room in the inpatient unit in order to provide a stool specimen at this visit.

Clinic breakfast

For the 5 participants being admitted 2 weeks prior to Celecoxib administration, the inpatient schedule is as follows:

Day 0

Usual diet

Stool sample +/- 1 day

Day 1

Usual diet

Day 2

Usual diet

Day 3

Stool sample +/- 1 day

Usual diet

Day 4

Usual diet

Day 5

Usual diet

Day 6

Usual diet

Day 7

Stool sample +/- 1 day

Usual diet

Day 8

Usual diet

Day 9

Usual diet

Day 10

Usual diet

Day 11

Usual diet

Stool sample (+/- 1 day)

Day 12

Usual diet

Day 13

Spot urine for PGE-M

24 hour urine for testing of the following: PGE-M, estrogen metabolites, creatinine, volume

NPO after 9 pm except water

Usual diet

Day 14

Usual diet

Fasting research labs- TNF- α , IL6, IL8, MCP-1, insulin, serum estradiol and estrogen metabolites, serum endocannabinoids

MSKCC labs: CBC, ESR, CMP, hsCRP, PT/PTT/INR, lipid panel, estradiol

Spot urine for PGE-M after completion of 24-hr urine collection

stool sample +/- 1 day

Fat biopsy

Start Celecoxib 200 mg PO BID

NPO after 9 pm except water

Day 15

Bod Pod

Usual diet

Continue Celecoxib 200 mg PO BID

Day 16

Usual diet

Continue Celecoxib 200 mg PO BID

Day 17

Usual diet

Continue Celecoxib 200 mg PO BID

Day 18

Usual diet

Continue Celecoxib 200 mg PO BID

Day 19

Usual diet

Continue Celecoxib 200 mg PO BID

Day 20

Usual diet

Continue Celecoxib 200 mg PO BID

Day 21

Usual diet

Continue Celecoxib 200 mg PO BID

Day 22

Usual diet

Continue Celecoxib 200 mg PO BID

Day 23

Spot urine for PGE-M

24 hour urine for testing of the following: PGE-M, estrogen metabolites, creatinine, volume

stool specimen +/- 1 day

Continue Celecoxib 200 mg PO BID

NPO after 9 pm except water

Day 24

Celecoxib 200 mg PO in AM

Fasting research lab: TNF- α , IL6, IL8, MCP-1, insulin, serum estradiol and estrogen metabolites, celecoxib level, serum endocannabinoids

MSKCC labs: CBC, ESR, CMP, PT/PTT/INR, hsCRP, lipid panel, estradiol

Spot urine for PGE-M after completion of 24 hour urine collection

Fat biopsy

Usual diet

Discharge from RUH

Dispense Tylenol 325mg #30 tablets.

Out-Patient Visit:

End of study visit (7-11 days after discharge)

Spot urine collection for PGE-M

Research labs: serum estradiol and estrogen metabolites, serum endocannabinoids

MSKCC labs: hsCRP, estradiol

Stool collection- Patients will be given a room in the inpatient unit in order to provide a stool specimen at this visit.

Clinic breakfast

Methodology for Microbiota Analysis of Stool specimens

Approximately 5 grams of feces will be collected immediately after a bowel movement and rapidly frozen at -80° C.

For each fecal specimen, DNA will be extracted using a phenol-chloroform extraction technique with bead beating for mechanical disruption. The isolated DNA will be purified and then PCR amplified using modified universal primers for the V4-V5 portion of the 16s ribosomal RNA gene. The purified PCR products will be pooled and then barcoded following the Illumina TruSeq Sample Preparation protocol. The library will then be sequenced using the Illumina MiSeq sequencing platform.

The sequence data will be screened and filtered using Mothur before each sequence is classified using a modified inhouse database containing sequences from GreenGenes 99 and retrieved 16S sequences from Genbank. The relative abundance of the microbiota will be represented by the percentages of the classified taxa sequences out of the total sequences present in the sample. In addition to the classification of the raw sequences, sequences that fall into an operation taxonomic unit (OTU) with 97% similarity will also be classified.

Additionally, the biodiversity of the microbiota of a sample will be surveyed using the Shannon Diversity Index. The comparison of the biodiversity between samples will be measured by unweighted UNIFRAC distances and visually represented by the Principal Components Analysis. A LDA Effect Size (LEfSe) analysis can be completed to look for specific bacteria that may contribute to any differences seen between groups of samples.

12.8 * Data Analysis

Describe method(s) of data analysis. Include the role of external collaborators as appropriate.

With 10 subjects, we will be able to detect effect sizes larger than 1 with 80% power at 0.05 significance level on a 2-tail test

12.9 * Explain the rationale for the choice of statistical measures and the number of subjects proposed for the study, including the power calculations when applicable.

In a study including women across the BMI spectrum, the effect size for the pre vs post differences in PGE-M excretion was found to be 0.64 for current smokers, 1.06 for former smokers and 0.68 for non-smokers (17).

Mice data shows that baseline levels of PGE-M are twice as high in obese than lean mice and the reduction on PGE-M is 70% higher in obese mice. Based on this, we will power our study to detect an effect size of 1 in the decrease of PGE-M levels with treatment. Studies in obese mice have shown an almost 3-fold increase in excretion of PGE-M compared to lean mice ([name] unpublished observations).

To test if the measurement of PGE-M in the urine will decrease after administration of Celecoxib 200 mg BID a paired t-test will be used.

A similar approach will be used to test the secondary outcomes including PGE-2 in adipose tissue, cytokine levels (log-transformed), and estrogen metabolites. Decrease in outcomes will be correlated to identify which variable correlates with the primary outcome.

12.10 * Will samples be coded?

Yes No

If Yes, Please describe coding scheme consistent with GCP. If samples will not be coded, please provide justification for this proposed departure from GCP practice.

Samples will be coded without subject identifiers with a random number.

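### The Day 14 stool window lets the last stability sample, which is also the pre-drug baseline, fall after the first celecoxib dose, and no later sample can confirm stability at Day 14

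*Combined protocol and SAP*

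**What the plan says.** Section 12.1 (Overview) sets the question as "whether the fecal microbiota is stable after 3 or 7 days or needs 14 or more days" and says the answer will guide later studies of the same kind. Section 12.6 lists it as a secondary outcome: "Determination of the length of time to achieve stability of fecal microbiota". The sample is small: "We additionally plan to study the fecal microbiota of 5 of the 10 participants being studied".

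Section 12.7 admits these women 11 days early and adds stool collections: "4 additional stool samples will be collected at Days 0,3, 7, and 11, +/- 1 day". In the long-stay schedule the entries for Days 0, 3 and 7 read "Stool sample +/- 1 day", and the Day 14 stool has the same window. Day 14 also carries the entry "Start Celecoxib 200 mg PO BID". The next inpatient stool is on Day 23, "stool specimen +/- 1 day", while celecoxib continues. The last stool is at the outpatient visit, 7 to 11 days after discharge on Day 24.

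For analysis, the microbiota methods in Section 12.7 give relative abundances, the Shannon index and between-sample comparison by "unweighted UNIFRAC distances and visually represented by the Principal Components Analysis". A LEfSe analysis is optional. No section defines stability, sets a margin, or gives a precision or sample-size figure for this aim. Section 12.2 adds a second use of the stool data, namely whether celecoxib changes the microbiota. In the long-stay women, Day 14 is the planned pre-drug sample closest to treatment.

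**The concern.** The Day 14 sample does two jobs. It is the end of the drug-free series against which earlier days are judged, and it is the baseline for any celecoxib effect. If it is taken after dosing, a drug effect can pass for continuing drift in the first use and can be subtracted out of the second.

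The series also stops at Day 14. Showing that a day is stable requires at least one later sample under the same conditions. Days 3 and 7 have such samples and Day 14 has none.

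The result is meant to set baseline timing in future studies, and five women each spend 11 extra inpatient days for it (5 x 11 = 55 days). A conclusion that goes beyond what the samples support would be carried into those designs.

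**Working it through.** **Inputs from the long-stay schedule in Section 12.7.** Stool on Days 0, 3, 7, 11, 14 and 23, each +/- 1 day; first dose on Day 14; discharge on Day 24; final visit 7-11 days later.

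**Window against dosing.** The Day 14 window runs from 14 - 1 = 13 to 14 + 1 = 15.
- Day 13 is before the first dose.
- Day 14 may be before or after it, because the entry gives no clock order.
- Day 15 is after it.

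The gap between the Day 11 and Day 14 samples can range from 13 - 12 = 1 day to 15 - 10 = 5 days.

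**What follows Day 14.**
- Day 23 is 23 - 14 = 9 days into treatment, so time and drug are mixed.
- The final visit falls on Days 24 + 7 = 31 to 24 + 11 = 35. It is off drug but after at least a week away from the inpatient diet.

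**Which comparisons are available without drug and on the diet.**
- Day 3 against Days 7, 11 and 14: yes.
- Day 7 against Days 11 and 14: yes.
- Day 11 against Day 14: yes, one comparison.
- Day 14 against anything later: none.

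**The plan's own figure first.** Section 12.8 states 80% power for an effect size of 1 with 10 subjects, two-sided 0.05. For a paired t-test with df = n - 1 and noncentrality d x sqrt(n), n = 10 and d = 1 give noncentrality 3.16 and power 0.803. The stated figure reproduces.

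**The same formula at n = 5** (df = 4, critical t = 2.776), with d in SDs of the paired difference:
- d = 0.5: power 14%.
- d = 1 (noncentrality 2.24): power 40.1%, so a real shift of this size is non-significant about 60% of the time.
- 80% power requires d = 1.68.
- 95% CI half-width = 2.776 / sqrt(5) = 1.24 SD.

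**Equivalence at n = 5** (two one-sided tests at 0.05, true change zero): power is 29% for a margin of 1 SD, and 80% is reached only at a margin of about 1.60 SD.

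**Sensitivity to the SD.** The documents give no within-woman variability. If SD meant the per-sample SD with independent errors (an assumption), the SD of a difference would be sqrt(2) times larger. A shift of one per-sample SD would then be d = 1/1.41 = 0.71, with power of about 23%, and the shift detectable with 80% power would be 1.68 x 1.41, about 2.38 per-sample SDs.

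**The case against.** The strongest reply is that the aim can largely be met. The third answer in Section 12.1 is a single residual class, and the plan never undertakes to separate stability reached at Day 14 from stability reached later. All five planned days up to Day 14 are intended as pre-drug. If neither Day 3 nor Day 7 matches the later samples, the residual class follows. This stands. A reader might infer that the aim is unattainable or that one of the three answers cannot be identified; the documents do not support that. What is lost is confirmation at Day 14 and any estimate beyond it.

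A reader might also infer that the plan will declare stability from a plot or from a non-significant test. No section says so. UniFrac distances and the Shannon index are quantitative, the principal components display only shows them, and LEfSe is optional and described as a search for bacteria behind differences between groups of samples. The paired t-test is named in Section 12.9 for urinary PGE-M. A similar approach is extended to secondary outcomes, but the examples given do not include microbiota. The power figures above are therefore a guide to precision at n = 5, not the power of a stated analysis.

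It is also fair that this is one secondary outcome in a pilot study. That limits how much needs to change, but it does not remove the overlap between the window and dosing.

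**Conclusion.** The point holds in a limited form. The written window allows the Day 14 stool to follow the first celecoxib dose by up to a day, which would compromise both the last stability point and the pre-drug baseline. This follows from the schedule alone and needs no assumption. How often it would happen cannot be judged from the documents.

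With no later drug-free sample on the inpatient diet, the study can support a statement about Days 3 and 7 relative to Days 11-14. It cannot confirm stability at Day 14, and any longer time is censored.

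Five women give too little precision for absence of significance to count as stability: a half-width of 1.24 SD of the paired difference, and 40% power for a 1-SD shift. These sizes assume roughly normal paired differences and an SD that the documents do not supply. The plan gives no criterion for stability, so nothing in it guards against such a reading, although it does not propose one.

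**What to change.** 1. In the long-stay schedule, require the Day 14 stool before the first celecoxib dose, for example from Day 13 to Day 14 pre-dose, and record the collection time. A window of minus one to zero days is not enough by itself, because a Day 14 stool could still follow that day's first dose.
2. Flag any sample taken after the first dose and exclude it from the stability and baseline analyses.
3. Limit the conclusion to whether Day 3 or Day 7 already resembles Days 11-14. Treat the class of fourteen days or longer as residual and unconfirmed.
4. Report each woman's UniFrac distances between days, with mean distances and 95% CIs, and label the aim descriptive. State that non-significance will not be read as stability.
5. If a margin is used, fix it in advance and apply it to Days 3 and 7 only. With excess defined as distance(day, 14) - distance(11, 14), Day 11 gives zero by construction and would always pass. Report the Day 11-14 distance alongside, since drift over those days enlarges the reference and makes Days 3 and 7 easier to pass.

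No visit, sample or assay is added. The costs are a narrower claim, an occasional missing Day 14 sample when no stool is produced before dosing, and intervals that may be too wide to settle Day 3 or Day 7.
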